5.4 Treatment Assignment Procedures

The study statistician will create computer generated randomized treatment group allocations for each site. These randomized permuted blocks will be uploaded into REDCap to provide treatment group assignment. Following eligibility screening and informed consent documentation study staff will authorize participants for enrollment. Following this authorization (in REDCap) participants will be officially enrolled in the study and the REDCap system will then assign the next computer generated treatment group allocation (within site) to one of the two treatment conditions. Participants will be assigned in a 1:1 ratio to Oral Health and Healthy Lifestyle treatment groups.

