5.4.1 Randomization Procedures

Randomization codes will be generated by the study statistician. The randomization list containing treatment assignment codes will be retained by the study statistician and will not be accessible to study staff. This is an electronic document that will be uploaded into REDCap on NAU's secure server. Permuted blocks will prevent field staff from knowing what treatment the next participant will receive during the recruitment process and ensure approximately equal numbers of participants in each study arm at any given time during study enrollment.

No break of randomization codes is anticipated but if necessary could be done in collaboration with the study statistician. Separate permuted blocks will be generated for each of the two sites.

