conservative we round down to an even number of 282 (141 per group) which provides power of 0.71 for a 2-tailed test with alpha .05 and a 37% treatment group difference in dmfs. This sample size achieves power = 0.97 under the smaller standard deviation assumption. Current standards of care recommend FV application for all children at high risk for caries. Study staff will therefore apply FV to children in the Healthy Lifestyle group at 12 and 24 months of age. This will potentially dilute between groups caries differences but is a necessary accommodation given the high caries burden in AI communities.

We feel this is a statistically defensible target enrollment given the high fluoride varnish application frequency in our study and the ~ 2.5 years of follow-up time from birth. Moreover, genuine treatment effects occurring below our statistical detection threshold or within highly variable decay experiences are unlikely to be clinically and ecologically relevant. Both calculations are based upon the average effects of fluoride varnish alone⁹ and thus should be conservative. In this regard an Australian trial that enrolled expectant Aboriginal women suggests the combination of MI and fluoride varnish results in a larger treatment effect than varnish alone³ and that this difference persisted over 5 years of follow up.¹⁵ Power analysis based upon their data is presented in the section below.

On average 9 and 23 women per month give birth at Hopi and Crow, respectively. We target recruiting 7 per month at Hopi and 18 per month at Crow. This will achieve our target enrollment by 14 months and will accrue a larger number of participants at Crow (N=252) than Hopi (N=98). Our study is not designed to compare intervention effectiveness across tribes but rather across treatment groups. Therefore, the enrollment imbalance across sites does not affect our primary research question as both groups will be combined when evaluating all outcomes.

Secondary outcome power analysis

Secondary outcomes include a complementary caries measure and a set of caregiver-assessed health knowledge and behavior domains.

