12.4 Final Analysis Plan

Descriptive analyses will include calculating means and proportions and their associated measures of variability. We will also compare key sociodemographic differences across those who do and do not complete the study (attrition analysis). As per CONSORT guidelines¹⁷ we will not statistically compare participant baseline characteristics across treatment arms.

Missing data. We will multiply impute missing values for the primary outcome for all participants enrolled and randomly assigned to a treatment (intention to treat). We will impute within each treatment group¹⁸ based upon key sociodemographic factors (maternal age and education; tribe; child sex) assuming the data are missing at random. Multiply imputed estimates of regression coefficients and standard errors will be combined using Rubin's rules. The primary outcome is a continuous variable.

The focal intention to treat analysis of the intervention will be evaluated by regressing dmfs at follow up on a binary treatment group variable using robust variance estimates. We will include child sex, child age in months at follow up and site (Hopi/Crow) as covariates. Although randomization should balance the treatment groups, age and sex are strongly associated with dmfs scores⁷ and covarying those variables should increase efficiency. Covarying child age also statistically controls for follow up length. In contrast, covarying the (log) number of tooth surfaces in analysis of childhood caries did not predict dmfs in a similar RCT.² We are not powered to compare treatment differences across site but using site as a covariate will increase sensitivity in the context of possible site differences in caries.

Robust variance estimation in OLS regression will provide more accurate variance estimates in the presence of assumptive violation, i.e., heteroscedasticity. If the model is homoscedastic robust regression will provide estimates close to non-robust OLS estimates.¹⁹ This approach obviates the need to prespecify the correct form of assumptive violation.

Analysis of the oral health secondary outcome (dmft) will parallel dmfs analyses. Other secondary outcomes involving questionnaires will regress post-test scores (Visit 6) on a binary treatment indicator variable using baseline values as a covariate.

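### The model for the four questionnaire secondary outcomes leaves out site, the randomisation stratum, so reported standard errors are somewhat too large if Visit 6 scores still differ by site after baseline adjustment

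*Combined protocol and SAP*

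**What the plan says.** Section 5.4 fixes the allocation ratio: "Participants will be assigned in a 1:1 ratio to Oral Health and Healthy Lifestyle treatment groups". Section 5.4.1 stratifies it: "Separate permuted blocks will be generated for each of the two sites".

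Section 12.4 carries the stratum into the primary analysis: "We will include child sex, child age in months at follow up and site (Hopi/Crow) as covariates". The reason given is that "using site as a covariate will increase sensitivity in the context of possible site differences in caries". For the caries secondary outcome, "Analysis of the oral health secondary outcome (dmft) will parallel dmfs analyses", so dmft has the site term as well.

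The remaining four secondary outcomes get one sentence: "Other secondary outcomes involving questionnaires will regress post-test scores (Visit 6) on a binary treatment indicator variable using baseline values as a covariate". It names treatment and baseline only, and does not say whether robust variance applies.

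Section 12.2 expects 252 participants at Crow and 98 at Hopi, and says that "both groups will be combined when evaluating all outcomes".

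On timing, sections 3.2 and 4 place oral health knowledge and maternal/child health knowledge at Visits 1, 4, 5 and 6, attitudes at Visits 1, 4 and 6, and behavior at Visits 4, 5 and 6 only. The Protocol Summary nevertheless lists behavior among the outcomes to be compared as change from Visit 1.

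**The concern.** Blocking within site balances the arms inside each community, so a difference in level between Hopi and Crow contributes almost nothing to the treatment contrast. A model without site does not know this. It leaves the between-site variance in the residual and charges it to the standard error. The confidence interval is then wider than the sampling variation of the estimate warrants, and the test rejects less often than its nominal level.

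The plan accepts this reasoning for caries and then does not apply it to four of its five secondary outcomes, without giving a reason. Site differences in these scores are plausible: each site has its own community health representatives, one per arm (section 6.6.1), and recruitment channels differ (sections 5.3 and 7.1). Any difference that arises from delivery after Visit 1 cannot be removed by a Visit 1 score. If the site term is not prespecified, whether to add it could also be decided with the data in hand.

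**Working it through.** **Inputs from the documents.** Crow 252 and Hopi 98 of 350; 282 retained, 141 per arm (section 12.2); 1:1 allocation in blocks within site (sections 5.4 and 5.4.1); knowledge power of 0.81 for 65% against 80% correct (section 12.2).

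**Inputs assumed.** The residual site gap *d*, which is the Visit 6 difference between sites left after the fitted covariates, in residual SD units; equal retention at the two sites; a within-site correlation of 0.5 between baseline and Visit 6 where baseline is modelled.

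**Step 1: the plan's own figure.** Treat knowledge as two proportions, n = 141 per arm, two-sided alpha 0.05, pooled variance under the null. The mean proportion is 0.725.

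- Numerator: 0.15 × √141 − 1.96 × √(2 × 0.725 × 0.275) = 1.781 − 1.238 = 0.543
- Denominator: √(0.65 × 0.35 + 0.80 × 0.20) = 0.622
- Power = Φ(0.873) = 0.809, which reproduces 0.81. It is the only questionnaire outcome with a stated power.

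**Step 2: excess in the reported standard error.** The Crow share is 252/350 = 0.72, so the between-site variance is 0.72 × 0.28 × d² = 0.2016 d² in residual variance units. The ratio of the standard error without site to that with site is R = √(1 + 0.2016 d²). The true type I error at nominal 5% is 2 × [1 − Φ(1.96 R)].

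| d | R | Excess | True type I error |
|---|---|---|---|
| 0.2 | 1.004 | 0.4% | 0.049 |
| 0.3 | 1.009 | 0.9% | 0.048 |
| 0.5 | 1.025 | 2.5% | 0.045 |
| 1.0 | 1.096 | 9.6% | 0.032 |

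**Step 3: effect on power.** Take an effect with power of about 0.81 by t-test at 141 per arm, which is 0.339 SD. Its standardised size is 0.339 × √(141/2) = 2.848. The estimate itself is no noisier without site, so only the rejection threshold moves, and power is Φ(2.848 − 1.96 R).

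- With site: Φ(0.888) = 0.813
- Without site, d = 0.3: Φ(0.870) = 0.808
- Without site, d = 0.5: Φ(0.839) = 0.799
- Without site, d = 1.0: Φ(0.699) = 0.758

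**Step 4: check by simulation.** 282 mothers, stratified 1:1 assignment, ordinary least squares with and without site, 3,000 runs per scenario. With no baseline covariate, the standard error ratio was 1.004, 1.025 and 1.097 at d = 0.2, 0.5 and 1.0, in line with the formula. At d = 0.5 the actual SD of the estimate was 0.1195 under both models.

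**Step 5: what baseline adjustment absorbs.** Same simulation, with correlation 0.5 and gaps in raw within-site SD units:

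| Gap at Visit 1 | Gap at Visit 6 | Ratio |
|---|---|---|
| 0.5 | 0.25 | 1.000 |
| 0.5 | 0.5 | 1.008 |
| 1.0 | 1.0 | 1.027 |
| 0 | 0.5 | 1.033 |

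In the first row the Visit 6 gap is exactly what baseline predicts, and nothing is lost although the sites differ. The last row is a gap that opens after baseline.

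**Step 6: behavior.** With no Visit 1 score there is nothing to absorb the gap, so the table in step 2 applies with d equal to the whole Visit 6 site difference.

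**The case against.** The strongest reply is that the loss is small, depends on unknowns, and falls on secondary outcomes only. Much of this stands. The documents report no site gap and no SD for any questionnaire score, so every percentage above is conditional. The plan's reason for the site covariate is confined to caries, and site-specific materials and staff do not by themselves establish a gap in scores. The plan's target for knowledge is also not obviously at risk. If the score had an SD of 15 points (an assumption), the targeted 15-point difference would have a standard error of 15 × √(2/141) = 1.79 and a z of about 8.4. A 9.6% inflation still leaves about 7.7.

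A reader might infer three stronger things, and the documents support none of them:

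- That standard errors are too large whenever the two communities differ. Three of the four outcomes have a Visit 1 score in the model, and step 5 shows that it can absorb a site gap in part or entirely.
- That omitting site is equivalent to discarding some of the 282 mothers. The estimate has the same sampling variation under either model; only its reported precision is understated.
- That the questionnaire results would be biased or prone to false positives. Allocation is balanced within site, and the error runs toward too few rejections.

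What remains is that the stated model ignores the stratum, no reason is given, and including it costs almost nothing.

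**Conclusion.** The point holds as a matter of efficiency and consistency. Site is the randomisation stratum and is in the caries models but not in the questionnaire models. If Visit 6 scores differ by site after baseline adjustment, reported standard errors are too large: by less than 1% for a residual gap up to 0.3 SD, about 2.5% at 0.5 SD, and 9.6% only at a full 1.0 SD. The omission, its direction and the absence of bias follow from the documents and the design. The size does not, since it rests on assumed gaps and on the planned 72:28 split being retained.

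Behavior is the most exposed of the four outcomes. Its whole site gap stays in the residual, and the stated model cannot be fitted as written because the baseline value it calls for is never collected. The primary outcome and dmft are not affected. This is a free improvement, not a threat to the trial's conclusions.

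**What to change.** In section 12.4, replace the sentence on questionnaire outcomes with one that specifies:

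- oral health knowledge, attitudes and maternal/child health knowledge: Visit 6 score regressed on treatment, site (Hopi/Crow) and the Visit 1 value of the same score;
- oral health behavior: Visit 6 score regressed on treatment and site, with no baseline term. The Visit 4 score should not stand in for baseline, because it is measured after randomisation and after intervention sessions have begun;
- the same robust variance estimator as the primary model for all four. Robust variance alone does not replace the site term, because the between-site component would still be in the residuals.

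The Protocol Summary's description of behavior as a change from Visit 1 should be brought into line. The cost is a sentence or two in the plan and one degree of freedom per model out of about 280. No new data are needed, since site is known for every participant at randomisation.

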13 SOURCE DOCUMENTS AND ACCESS TO SOURCE DATA/DOCUMENTS

Study staff will maintain appropriate medical and research records for this study, in compliance with ICH E6, Section 4.9 and regulatory and institutional requirements for the protection of confidentiality of participants. Study staff will permit authorized representatives of NIDCR and regulatory agencies to examine (and when required by applicable law, to copy) research records for the purposes of quality assurance reviews, audits, and evaluation of the study safety, progress, and data validity.

Source documents will include both paper and electronic data forms. Paper data forms include informed consent forms, encounter forms, and SAE and UP report forms. Electronic data forms include sociodemographic and oral health survey data, dental assessment data, and IHS dental and health records. Consent forms will be kept in locked file cabinets, separate from all other participant records. Identifying information such as name, address, and phone number will be maintained on each mother or caregiver/child in the study for the purposes of recontact and follow-up. This information will be kept in locked file cabinets in the study field offices.

The web-based Clinical Trials Management Software (CTMS) system REDCap will be the original source for scheduled and actual study visits; questionnaire data; adverse event reports, and protocol deviations. Data from other sources (dental assessment data) will be uploaded into REDCap. These data will be kept on a secure password-protected server (ADAMS) accessible only to project staff.

Whenever possible, data will be entered directly into an iPad. Based on available data, the rate of possible system failure is estimated at <1%. In the eventuality of a system outage or internet service failure, back-up paper forms for data capture and subsequent system entry are available.

14 QUALITY CONTROL AND QUALITY ASSURANCE

The PI has the ultimate responsibility for implementing and maintaining quality assurance and quality control systems with written operating procedures to ensure that the trial is conducted and data are generated, documented and reported in compliance with the protocol. The Fidelity Monitoring Coordinator and Data Collection Coordinator will provide regular reports on the fidelity and administration of the intervention to the PI.

The study team leadership will meet monthly to ensure the intervention trial is meeting objectives and to consider all aspects of the project for oversight, feedback and suggestions enhancing future progress along with monitoring of expenditures and cost allocations as the project progresses. Their oversight includes verification that the PI has secured appropriate agreements from all involved parties, has adequately secured the data/documents and reports and all protocols and standard operating procedures have been followed and quality assurance and quality control of the data, its reliability and assessment have been appropriately recorded, maintained and evaluated during the intervention trial.

The PI and key personnel will have oversight responsibility to ensure compliance of the intervention trial with the protocols, the accuracy and completeness of the documents, reports, notes, etc. and quality management of the overall intervention program.

The Data Collection Coordinator will serve as the Quality Management Coordinator and will utilize clinical trials monitoring systems available through REDCap, NIDCR and study documents to monitor quality control of all study activities. This will include the documentation and maintenance of records, and generation of regular reports for both internal (within study team) and quarterly and/or annual reports, as scheduled, to the NIDCR. These will provide the status of study preparation (including CHR trainings, dental examiner trainings and calibration sessions and results) and study activities (including participant recruitment, activities completion including intervention deliveries by sites, incentives dispersal, and data (withdrawals) and safety (AE, SAE) monitoring). All of these major activities will utilize checklists to ensure and document completion of procedures. (More details can be found in the Data Management Plan and the Quality Management Plan).

A. Recruitment and tracking. NAU staff and CHRs at Hopi and Crow will be trained on procedures and scripts, will use eligibility checklists, and will document study eligibility. Participant personal identifying information will be maintained in a secure location (REDCap) to allow tracking across study activities.

B. Consent procedures. Informed consent will be obtained by Site Coordinators at Hopi and Crow. Participants will complete paper consents, and consents will be collected and stored in locked files. Documentation of informed consent will be maintained in REDCap.

C. Assessment completion. All study staff will be trained to complete data collection processes. All staff trainings will be documented as to activity and date completed. Assessment completion will be overseen and recorded by date in REDCap. 1) CHRs will be trained to administer questionnaires using mobile devices via REDCap 2) The

dental assessor will conduct the oral assessment and the CHR will enter dental assessment data into REDCap.

D. Intervention training, delivery, and fidelity monitoring. Study interventions will be delivered by CHR facilitators who are trained by study investigators/personnel and evaluated for fidelity to the intervention plan. Training binders and toolboxes will be utilized to increase standardization and fidelity. All trainings will be documented. New CHRs will receive the same training. All intervention sessions will be documented and audiotaped for fidelity monitoring purposes. Facilitators will receive feedback to address any issues identified in the fidelity evaluation.

E. Examiner training and calibration. Persons performing the oral assessments will attend trainings and calibration sessions conducted by our oral health training team. We will model calibration procedures found in Warren et al.¹⁶ These are described in the MOP.

15 ETHICS/PROTECTION OF HUMAN SUBJECTS

15.1 Ethical Standard

The investigator will ensure that this study is conducted in full conformity with the principles set forth in The Belmont Report: Ethical Principles and Guidelines for the Protection of Human Subjects of Research, as drafted by the US National Commission for the Protection of Human Subjects of Biomedical and Behavioral Research (April 18, 1979) and codified in 45 CFR Part 46 and/or the ICH E6.

15.2 Institutional Review Board

The protocol, informed consent form(s), recruitment materials, and all participant materials will be submitted to the NAU, Phoenix Area IHS and the Rocky Mountain Tribal IRBs for review and approval. Approval of both the protocol and the consent form(s) must be obtained before any participant is enrolled. Any amendment to the protocol will require review and approval by the IRBs before the changes are implemented in the study.

15.3 Informed Consent Process

Informed consent is a process that is initiated prior to the individual's agreeing to participate in the study and continues throughout the individual's study participation. Extensive discussion of risks and benefits of participation in the study will be provided to the mothers/caregivers and their families. Consent forms describing in detail the healthy lifestyle and the MI intervention, study duration and procedures, and risks and benefits will be given to the mothers, and written documentation of informed consent will be required prior to starting the study.

All adult participants will be required to sign a written consent form before participating in the study. Verbal consent will not be accepted. A form with contact information for the study PI and Project Coordinators will be provided to each participant. Participants will be given an orientation to the project, including intervention schedule, study risks and benefits, and compensation information. All participants will have adequate time to ask questions or request more information

Extensive discussion of risks and possible benefits of study participation will be provided to participants and their families, if applicable. A consent form describing in detail the study procedures and risks will be given to the participant. Consent forms will be IRB-approved, and the participant is required to read and review the document or have the document read to him or her. The participant will sign the informed consent document prior to any study-related assessments or procedures. Participants will be given the opportunity to discuss the study with others or think about it prior to agreeing to participate. They may withdraw consent at any time throughout the course of the study. A copy of the signed informed consent document will be given to participants for their records. The rights and welfare of the participants will be protected by emphasizing

to them that the quality of their clinical care will not be adversely affected if they decline to participate in this study.

Consent forms will be required for the calibration participants and expectant mother participants, who also consent for their babies in their original baseline consent forms. Re-consent is necessary only in the event of a protocol change.

The consent process will be documented in REDCap.

